Protocol

1. Project Title

Effects of acute intermittent hypoxia on sensory function in healthy adults

2. Investigator(s):

[name]
[name]
[name]

3. Abstract:

Exposure to acute intermittent hypoxia (AIH) has safely induced facilitation of motor output in human studies. Despite this study, the affects of AIH on sensory function has not been established. We will use a commercially-available hypoxicicator that can be programmed to achieve a targeted level of arterial oxygen saturation. We plan to compare 3 previously published protocols that have generated motor facilitation (and a sham condition) to characterize and effects on sensory function in healthy adults. Primary outcomes will be measures of sensory function (thresholds and tolerance).

4. Background:

Brief intermittent episodes of hypoxia (or acute intermittent hypoxia [AIH]) induce plasticity in muscle motor neurons [1]. AIH activates carotid chemo afferents that stimulate episodic serotonin release [2, 3] which subsequently strengthens synaptic input and motor output of motor nuclei [3-8]. The persistent increase in phrenic nerve burst amplitude following repeated exposure to AIH is termed long-term facilitation (LTF) [9]. For example, increases in breathing capacity as demonstrated by a significant increase in minute volume has been demonstrated after exposure to AIH in unanesthetized and anesthetized rats [10, 11].

AIH has been demonstrated to be safe in healthy persons and has been routinely used in training athletes for many years. Similarly AIH is safe for people with neurological dysfunction (eg patients with chronic spinal cord injury (SCI)). In these patients, a single exposure to IH increased ankle plantar flexion torque by more than 80% [12]. Significant improvements in 10 meter walk times and 6 minute walk distances have been seen in patients with chronic SCI when IH was combined with walking at maximal sustainable exertion for 30 minutes [13].

Despite this promising work, the effect of AIH on sensory function has not been determined in humans, making this proposal a logical progression of the promising work done to date in improving motor function.

5. Specific Aims:

Our aim is to characterize how exposure to AIH protocols shown to enhance motor function impacts sensory function.

6. Research Plan:

Participants who meet the eligibility criteria and provide written consent to participate will be enrolled. This includes a pregnancy test for female volunteers that will be performed on the first day. Each participant will complete 3 different protocols of AIH delivery based on protocols derived from the literature that have been used to enhance motor function as well as a sham condition. Each delivery and testing session will last approximately 2 hours and be separated by at least 24 hours.

Inclusion criteria

Male and female participants between the ages of 18-40 years will be eligible to participate in the study unless they meet any of the following criteria.

Exclusion criteria

- a. Diagnosis of cardiovascular disease (Hypertension, arrhythmias, coronary artery disease, congenital and valvar heart diseases)
- b. Diagnosis of neuromuscular disease
- c. Diagnosis of any neurological disease
- d. Presence of concurrent medical illness including infection, fractures
- e. Diagnosis of obstructive sleep apnea
- f. Diagnosis of obstructive/restrictive lung disease
- g. Diagnosis of exercise induced asthma
- h. FEV1/FVC<80% and/or FVC<80% of predicted value indicating airway obstruction
- i. Subjects on prednisolone therapy or selective serotonin reuptake inhibitor (SSRI) therapy will be excluded from the study as these pharmacological agents are known to amplify the effects of IH[22, 23]
- j. Diagnosis of epilepsy or history of seizures and attention deficit disorders
- k. Pregnancy
- l. Diabetes
- m. History of coagulation disorders
- n. History of chronic pain
- o. Body mass index(BMI)> 35kg/m²
- p. Subjects on prescription medicines such as beta blockers and other drugs that are prescribed in any of the exclusionary disorders listed above.

Intervention

We will use a commercially-available hypoxicator that can be programmed to achieve a targeted level of arterial oxygen saturation. The fraction of inspired oxygen (FiO₂) during the hypoxic episodes will be adjusted to maintain pulse oximetry (SPO₂) between 80%-

90%. In our experience, this can be achieved with a FiO₂ in the range of 9%-11 %. FiO₂ levels of 9% and 11% correspond to O₂ concentrations in room air at altitudes of 6500 meters and 5000 meters respectively, both altitudes humans are exposed to while on trekking expeditions and also have permanent human habitation [29, 30]. We will use alternating phases of hypoxia (FiO₂ :9%-11%) and normoxic or hyperoxic oxygen saturation with an FiO₂ between 22%-38%, based on the previous protocols used in human studies of motor function.

- A. 15 bouts of hypoxia for 1 minute, normoxia to hyperoxia 1 minute (Trumbower et al [12])
- B. 15 bouts of hypoxia for 2 minutes, normoxia to hyperoxia 1 minute (Hayes et al [13])
- C. 8 bouts of hypoxia for 2 minutes, normoxia to hyperoxia 1 minute (Tester et al [14])
- D. Sham hyperoxia (normoxia) for 2 minutes, normoxia to hyperoxia 1 minute

The order of the protocol will be randomly assigned for each participant who will remain blinded to the actual protocol they are receiving. All measures will be collected by a research assistant blinded to protocol assignment.

Outcomes

We propose to collect standardized measures of sensory function. Measures will be assessed at the hand and foot at baseline, immediately post- and every 10 minutes for 60 minutes after the AIH protocol.

Tactile:

Semmes-Weinstein filaments will be used to assess sensory thresholds. The patient will be in sitting position with shoes and socks removed. Starting with the weakest plastic kept perpendicular to the skin surface force will slowly be applied until there is a slight bend in the filament. The participant will indicate if they feel pressure. If not, the next filament is used and testing proceeds until the thinnest fiber that the participant can perceive is reached.

Pain sensitivity:

Participants will undergo quantitative sensory testing (QST) to determine pain sensitivity to thermal and pressure stimuli, as per protocols in our preliminary studies.

Study participants will undergo standard psychophysical pain testing using a contact thermode to deliver the evoked, thermal pain stimuli. The stimuli are to be applied by a research assistant who ensures proper thermode application and the range of stimulus intensities to be used (40-51°C) will be presented beforehand in ascending one-degree steps to each subject. We have found this procedure to be useful because it familiarizes subjects with the stimulus range, tends to obviate range effects in psychophysical scaling, and helps alleviate subject anxiety about the upper limit of stimulus intensities to be used. In order to standardize the scaling instructions and to clarify the distinction between the sensory intensity and affective dimensions of pain, a standardized instructional set will be used for all subjects. The research assistant will record numeric rating scale (NRS) response to each stimulus. The NRS will consist of a scale whose endpoints are

Protocol

Page 3 of 6

IRB version 03.09.04

PI version 3/18/2021 8:27 PM

designated as '0 - no pain sensation' and '100 - the most intense pain sensation imaginable'. In order to standardize the scaling instructions, standard instructions will be used for all participants.

Threshold and Tolerance. A continuous heat stimulus will be delivered to the subjects' dominant arm. The stimulus started at 35°C and will be increased at a rate of 0.5°C with subjects terminating the stimulus when the temperature reached pain threshold ("when the sensation first transitions from heat to pain") and tolerance ("when the sensation becomes so strong you want to remove it from your skin"). These procedures will be repeated three times and the average threshold and tolerance will be calculated.

Threshold and tolerance measures will also be collected using mechanical pressure applied using a Fischer Dolorimeter (Pain Diagnostics, Great Neck, NY). The tip of the dolorimeter is equipped with a rubber foot-plate of 1-cm diameter. During Dolorimeter testing, force is slowly increased until the subject indicates that the sensation changes from pressure to pain. Subjects are asked to rate any pain they are experiencing using a numeric rating scale (NRS) anchored at 0 (no pain sensation at all) and 100 (worst pain imaginable). Dolorimetry measures are made in the hand (1st dorsal interosseus muscle) and between the first and second toe on the dorsal aspect of the foot.

Temporal summation. A train of 6 heat pulses will be applied to the glabrous skin of the foot. To ensure temporal summation, an inter-stimulus interval of 2 seconds will be used with temperatures starting at 39°C and increasing to 50°C (the TSA medoc maintains 10°C/sec rate in this range which is sufficient for maintaining the desired inter-stimulus interval). The participants will be asked to rate the magnitude of their delayed (second) pain sensation following each heat pulse. These response ratings are believed to be primarily C-fiber mediated.^{35,36}

We will test effects protocol using a two way (protocol and time) analysis of covariance with sensory measures as the dependent variables. Demographic variables that show an association with the sensory measures in our sample (eg gender differences have mixed evidence related to differences in sensory report) will be included as covariates.

7. Possible Discomforts and Risks:

Evoked pain: Risk of injury with this testing is minimal in that they are widely used and safe procedures. While pain is produced, risk to the individual is minimal, because 1) the pain is transient in nature and generally subsides immediately after the procedure; 2) subjects are instructed that they may stop any procedure at any time with no adverse consequences; 3) the level of pain experienced by subjects is below their tolerance level; 4) this pain will only last as long as the stimulus is applied (which is under the control of the study participant); 5) thermal stimulus intensity will not cause any damage to the study participant's skin. Some study participants will feel pain after the painful stimulus is removed, but no long-lasting pain perception (i.e. longer than 90s) is expected from quantitative sensory testing. Similarly a slight risk of burn is involved using thermal stimuli. The thermal stimulator

(Medoc TSA) has a built in shut off threshold that prevents the delivery of temperatures over 51 deg C. Our group has completed more than 1000 testing sessions in the past 5 years without any adverse events.

Acute intermittent hypoxia: Our experiment is modeled from past human studies that have delivered similar doses of hypoxia that was considered safe and sufficient to elicit an increase in physiological response [12, 13, 14]. Moderate reductions in inspired oxygen can cause light-headedness, dizziness, reduced vision, and euphoria. We will continuously monitor the subject's heart rate, respiratory rate, and oxygen saturation (SPO2) to ensure that the administered oxygen levels remain within the targeted range (80- 85%). In an unlikely circumstance where the heart rate drops below 50 BPM or rises more than 150 BPM and/or systolic blood pressure drops below 85mm Hg or increases beyond 150mmHg, IH intervention will be stopped. If SPO2 falls below 75% or if subjects complain of light headedness, dizziness and reduced vision, the IH intervention will be terminated and supplemental O2 will be provided. In addition, the hypoxicator has a built in, feedback based, safety mechanism. In a circumstance of desaturation below a pre-set threshold of 80%, the hypoxicator switches to deliver hyperoxic air to increase saturation above the minimum set threshold of 80%.

8. Possible Benefits:

There is no direct benefit expected for any of the participants. Potential future benefits to the public include an increased knowledge of the effects of IH, which may eventually lead to the future treatments for neuromotor diseases.

9. Conflict of Interest:

We declare no conflicts of interest.

References

1. Gonzalez-Rothi, E.J., et al., Intermittent Hypoxia and Neurorehabilitation. *J Appl Physiol* (1985), 2015: p. 00235 2015.
2. MacFarlane, P.M. and G.S. Mitchell, Episodic spinal serotonin receptor activation elicits long-lasting phrenic motor facilitation by an NADPH oxidase-dependent mechanism. *J Physiol*, 2009. 587(Pt 22): p. 5469-81.
3. Fuller, D.D., et al., Synaptic pathways to phrenic motoneurons are enhanced by chronic intermittent hypoxia after cervical spinal cord injury. *J Neurosci*, 2003. 23(7): p. 2993- 3000.
4. Baker-Herman, T.L., et al., BDNF is necessary and sufficient for spinal respiratory plasticity following intermittent hypoxia. *Nature neuroscience*, 2004. 7(1): p. 48-55.

5. Lovett-Barr, M.R., et al., Repetitive intermittent hypoxia induces respiratory and somatic motor recovery after chronic cervical spinal injury. *J Neurosci*, 2012. 32(11): p. 3591-600.

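### Thresholds and tolerances are primary as a class, with no lead endpoint, alpha, multiplicity rule, sham contrast or stated role for the session baseline

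*Combined protocol and SAP*

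**What the plan says.** - **Primary outcomes.** Section 3 (Abstract): "Primary outcomes will be measures of sensory function (thresholds and tolerance". This is a plural class. No measure, site or time is singled out.
- **Comparison and aim.** The Abstract also says "We plan to compare 3 previously published protocols that have generated motor facilitation (and a sham condition". Section 5 (Specific Aims) says "Our aim is to characterize how exposure to AIH protocols shown to enhance motor function impacts sensory function".
- **Sites and times.** Section 6, Outcomes: "Measures will be assessed at the hand and foot at baseline, immediately post- and every 10 minutes for 60 minutes after the AIH protocol". That is one baseline and seven post-exposure times in each session.
- **Heat.** Section 6, Threshold and Tolerance: "A continuous heat stimulus will be delivered to the subjects' dominant arm", and "These procedures will be repeated three times and the average threshold and tolerance will be calculated".
- **Pressure.** The same part says "Threshold and tolerance measures will also be collected using mechanical pressure", at one hand site and one foot site. The procedure it describes ends at the threshold: "force is slowly increased until the subject indicates that the sensation changes from pressure to pain".
- **Analysis.** The last paragraph of Section 6 before Section 7 specifies a two-way analysis of covariance, with protocol and time as factors and the sensory measures as dependent variables. The only covariates it mentions are demographic variables found to be associated with the outcomes. No alpha, sample size, power, multiplicity rule, pairwise contrast or success criterion appears anywhere.

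**The concern.** The outcomes are labelled primary and the plan says that protocol effects will be tested. If one of about eight endpoints reaches p<0.05, nothing in the plan separates a finding from a chance result. The choice of which endpoint to stress would be made after the data are seen.

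Two further gaps concern what the test means:

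1. With four conditions, the protocol effect has 3 degrees of freedom. It can be significant because two hypoxia protocols differ from each other while neither differs from sham, so it does not by itself answer the question for which the sham was included.
2. Baseline is listed among the assessment times and is not named as a covariate, so it may enter the model as one of eight levels of time. The protocol main effect would then average in a value taken before exposure. Even if baseline is left out of time, its information is unused unless the model adjusts for it.

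**Working it through.** The plan states no error rate, power or sample size, so there is no figure of its own to reproduce.

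**Step 1. Count the endpoints (Section 6).**

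| Measure | Sites | Endpoints |
|---|---|---|
| Tactile threshold | hand, foot | 2 |
| Heat threshold and tolerance | dominant arm | 2 |
| Pressure threshold and tolerance | hand, foot | 4 |
| Total | | 8 |

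The count falls to 6 if pressure tolerance is left out because no procedure for it is described, or if the tactile measure is left out. It rises to 10 if heat is tested at hand and foot, as the general sentence in Outcomes implies.

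**Step 2. Chance of at least one false-positive protocol test.** Assumptions: 0.05 per test, one protocol test per endpoint, no true effect, and any one significant test read as positive.

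For independent endpoints the formula is 1 - 0.95^k:
- k=6: 0.265
- k=8: 0.337
- k=10: 0.401

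For correlated endpoints, repeated-measures F-tests were simulated with 4 conditions, n=20 assumed, equal correlation between endpoints, sphericity and 40,000 draws:

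| Endpoints | Corr. 0 | 0.3 | 0.5 | 0.7 | 0.9 |
|---|---|---|---|---|---|
| 6 | 26.6% | 24.6% | 21.6% | 17.1% | 11.4% |
| 8 | 33.8% | 30.8% | 26.6% | 20.5% | 12.8% |
| 10 | 40.1% | 36.1% | 30.4% | 23.1% | 13.6% |

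At correlations 0 and 0.9, runs with n=10 and n=40 agree to within about one percentage point.

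**Step 3. What the role of baseline does to one sham contrast.** Assumptions: an effect constant over the 7 post-exposure times, compound symmetry with within-session correlation r after participant effects are removed, n=20, and 3(n-1)=57 error df. The variance per session, scaled to an effect of 1, is:

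- Post-exposure mean with session baseline as covariate: (1+6r)/7 - r²
- Main effect with baseline as one of 8 times: [(1+7r)/8] / (7/8)²
- Post-exposure mean, unadjusted: (1+6r)/7
- Pre/post-by-protocol contrast: (1+6r)/7 + 1 - 2r

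Example at r=0.5: the first is 0.571 - 0.25 = 0.321 and the second is 0.5625/0.7656 = 0.735, a ratio of 0.437. At 57 df, 80% power at two-sided 0.05 needs a noncentrality of 2.85. Then 2.85 × √0.437 = 1.88, which gives 46%.

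Power where the covariate analysis has 80%:

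| Analysis | r=0 | 0.1 | 0.3 | 0.5 | 0.7 |
|---|---|---|---|---|---|
| Main effect, baseline averaged in | 75% | 70% | 59% | 46% | 30% |
| Baseline dropped from time, not adjusted for | 80% | 78% | 69% | 56% | 37% |
| Pre/post-by-protocol contrast | 17% | 25% | 42% | 56% | 67% |

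At r = 0.3, 0.5 and 0.7, averaging baseline in costs about 10, 10 and 7 points (row 2 minus row 1). Not adjusting for it costs about 11, 24 and 43 points (80% minus row 2).

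**Step 4. Power cost of multiplicity control.** Start from an illustrative 80% for one contrast at unadjusted 0.05. Dunnett over three sham contrasts has critical value 2.41 at 57 df (0.019 per contrast) and gives about 67%. Holm over 3 × 8 = 24 contrasts starts at 0.05/24 = 0.0021 and gives about 35-37% at that first step for n=12 to 30. Later Holm steps are less strict.

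**The case against.** The strongest reply is that this is a characterization study in healthy volunteers. It has no hypothesis, success criterion or confirmatory claim, so a familywise error rate is a standard it never set itself. Much of that stands. A reader might infer from the table in Step 2 that the plan has a 13-34% type I error. The documents do not support this: the alpha, the correlations and the any-one-significant rule are all assumptions of this review. What remains is that the outcomes are called primary and are to be tested, with nothing to say how one significant result among several is to be read.

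A reader might also infer that treating baseline as a level of time cuts power from 80% to as little as 30%. That does not follow either. Most of the loss at higher r comes from not adjusting for baseline, not from averaging it in. The loss is small at low r, which is possible once participant effects are removed in a crossover. The model also has two factors: if protocol-by-time is part of it, a focused pre/post contrast outperforms the main effect at r=0.5 and 0.7, though it does worse at low r and an omnibus interaction test would be weaker. The plan does not say which effect is the primary test.

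Finally, choosing a single endpoint has no basis in the documents and sits awkwardly with an aim to characterize. That is a fair argument for offering a descriptive route, but not for leaving the plan silent.

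**Conclusion.** The point holds in conditional form and should be addressed. The plan makes about 8 endpoints primary (6 to 10 by reading) and tests them without a lead endpoint, alpha or multiplicity rule. If any one protocol test at 0.05 were taken as a positive primary result, the false-positive chance would be about 13-34% for 8 endpoints and about 11-40% across 6 to 10, for between-endpoint correlation 0.9 to 0. Even the low end is more than twice 5%.

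Two parts need no error-rate assumption: the 3-df protocol test does not isolate sham, and the session baseline has no defined role. Under the Step 3 model, adjusting for session baseline does at least as well as each of the three alternatives at every r examined. The size of the gain depends on r, which the plan does not give.

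**What to change.** In the analysis paragraph of Section 6:

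1. Analyse the post-exposure measurements over stated times, with that session's baseline as a covariate and not as a level of time.
2. State the alpha, and test A, B and C each against sham with Dunnett or Holm.
3. Choose one route:
   - (a) name one primary endpoint by measure and site, and label the rest secondary;
   - (b) list all endpoints as primary and apply Holm across all sham contrasts (24 for 8 endpoints);
   - (c) say that the study is descriptive, report estimates with confidence intervals, and make no significance claim on any single endpoint.
4. Keep protocol-by-time as a pre-stated secondary analysis of the time course.
5. Reconcile the heat site (dominant arm under Threshold and Tolerance, hand and foot under Outcomes) before naming a heat endpoint.

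The cost is wording and analysis only, since baseline is already collected in each session. On the illustrative 80% scale, (a) leaves about 67% per contrast and takes primary status from the other endpoints. Route (b) leaves about 35-37% at Holm's first step. Route (c) gives up significance claims, needs the least text and fits the stated aim most closely.

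### Do the unequal exposure lengths, which no single sham length can match, call for a common baseline-to-first-post interval?

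*Combined protocol and SAP*

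**What the plan says.** Section 6, Intervention, lists four conditions, all received by each participant in random order:

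- "A. 15 bouts of hypoxia for 1 minute, normoxia to hyperoxia 1 minute"
- "B. 15 bouts of hypoxia for 2 minutes, normoxia to hyperoxia 1 minute"
- "C. 8 bouts of hypoxia for 2 minutes, normoxia to hyperoxia 1 minute"
- "D. Sham hyperoxia (normoxia) for 2 minutes, normoxia to hyperoxia 1 minute"

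The sham line has a cycle but no count, and it gives its 2-minute phase two gas labels.

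Under Outcomes, measures are taken "at baseline, immediately post- and every 10 minutes for 60 minutes after the AIH protocol". The post clock therefore starts when exposure ends. The text does not say how long before the first bout baseline is taken.

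The analysis paragraph that closes section 6 plans a two-way analysis of covariance with protocol and time as factors. It does not say how time is coded or what role baseline plays, and elapsed time is not named as a covariate. Section 6 also states "Each delivery and testing session will last approximately 2 hours", and says of the participant "who will remain blinded to the actual protocol they are receiving".

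**The concern.** Exposure length is tied to protocol in every session, so randomising the order of sessions cannot balance it. If a sensory threshold moves with time since baseline for reasons unrelated to hypoxia (sitting still, skin temperature, attention), the longer protocol has had more of that movement by its first post measure. With time coded as baseline, 0, 10, … 60 minutes post, such drift would sit inside the protocol-by-time terms and could pass for a protocol effect. The contrasts at stake are those the study wants: each protocol against sham, and the protocols against each other. A sham of undeclared length appears to leave the plan without a proper control for it.

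**Working it through.** **Exposure lengths.** Inputs are the bout counts and phase lengths under Intervention. Length = bouts × (hypoxia + recovery).

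- A: 15 × (1 + 1) = 30 min
- B: 15 × (2 + 1) = 45 min
- C: 8 × (2 + 1) = 24 min
- Sham with k cycles: 3k min, k not stated

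Dropping the last recovery minute gives 29, 44 and 23 min and leaves the differences unchanged.

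**Time from baseline to the seven post measures**, assuming baseline directly precedes the first bout: A 30–90, B 45–105, C 24–84 min. The gaps are the same at every post time: B−C 21, B−A 15, A−C 6 min.

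**Can a sham length remove the gap?** The largest absolute mismatch with A, B and C is:

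| Cycles k | Length (min) | Worst mismatch (min) |
|---|---|---|
| 8 | 24 | 21 |
| 10 | 30 | 15 |
| 11 | 33 | 12 |
| 12 | 36 | 12 |
| 15 | 45 | 21 |

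The minimum is 12 min. Eight cycles match C only, ten match A only and fifteen match B only. Below eight cycles the spread over all four conditions exceeds 21 min.

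**What the gap could do.** With linear drift of d per 10 min, B−C shifts by 2.1d, B−A by 1.5d and A−C by 0.6d. The documents give no value for d. For an assumed drift that levels off, 1 − exp(−t/τ), the B−C shift as a fraction of the plateau is:

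| τ (min) | At end of exposure | 60 min later |
|---|---|---|
| 10 | 0.08 | 0.00 |
| 20 | 0.20 | 0.01 |
| 40 | 0.22 | 0.05 |
| 80 | 0.17 | 0.08 |

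**What is already balanced.** Each session has one baseline and seven post batteries, the latter 10 min apart. At any given post time a participant has had the same number of noxious tests under every protocol. Habituation or sensitisation that follows the number of tests is therefore aligned. What remains is change over one untested interval of 24 to 45 min. Section 7 expects no evoked pain to last beyond 90 seconds, so carry-over pain from the baseline battery should be gone in all conditions, although other drift is not excluded.

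**Remedy 1: a wait before the first bout, to equalise the interval at 45 min.** The wait would be 45 − 30 = 15 min for A, 0 for B, 45 − 24 = 21 min for C and 45 − 3k for the sham (k up to 15). Every session then needs 45 + 60 = 105 min from the end of baseline to the start of the last battery, plus two batteries of b min each, plus set-up. Battery length is not stated; as an assumed range, b = 5, 7.5 and 10 give 115, 120 and 125 min before set-up. Protocol B is already this tight; the wait would make all four sessions so.

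**Remedy 2: a straight-line elapsed-time adjustment estimated from the sham.** Fit a line to the sham at times 0, 3k, 3k + 10, …, 3k + 60 and subtract 21 × slope from B−C. Under the levelling-off drift above, with τ = 10, 20, 40, 80 and k = 8, 10, 15:

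- Over all seven post times (4 × 3 × 7 = 84 cases) the adjusted error is larger in absolute size than the unadjusted one in 45. Mean absolute error rises from 0.082 to 0.106 of the plateau.
- At 0, 20 and 60 min post (36 cases) it is larger in 18.
- Example: τ = 20, k = 8, 60 min post. Unadjusted error is exp(−84/20) − exp(−105/20) = 0.010. The fitted correction is about 0.215, leaving −0.205.
- It does help at the end of exposure for τ = 20 to 80; for τ = 40, k = 8, 0.224 falls to 0.017.

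**The case for a change.** The strongest case for acting is that drift linear in elapsed time cannot be separated from protocol by the planned model. In a post-only protocol-plus-time model, in the saturated four-by-eight model, and in an additive model with protocol-specific baseline-to-post shifts, adding elapsed time leaves the model rank unchanged (10, 32 and 14). The drift becomes estimable only by assuming no protocol-by-time interaction, or a sham that changes with clock time alone; the first gives away a target of the study, and the second is unsafe while the sham gas carries two labels. The outcomes rest on participants' reports, and a levelling drift would look like a transient protocol effect. On this view only design can protect the contrasts, and a wait alters no bout.

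The algebra stands, and so does the point about randomised order. The step to a required change does not. It needs baseline to be taken just before exposure, time to be coded categorically with baseline as a level, and material clock-time drift apart from repeated-testing effects; the documents supply none of these. The wait also replaces one protocol-linked timing difference with another: baseline would precede the first bout by 15, 0, 21 or 45 − 3k min according to protocol, and the length of the wait could itself be a cue to participants meant to be blinded. Unequal exposure lengths may be such a cue already, so this cost is a matter of degree.

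**Conclusion.** No change to the plan. The 21-minute gap between B and C is exact if baseline directly precedes the first bout, and no sham length does better than a 12-minute worst mismatch. Unequal durations come with the aim of comparing three published protocols, and timing post measures from the end of exposure is a sensible alignment. Whether the gap biases anything depends on a clock-time drift whose size the documents do not give; the fractions above rest on an assumed drift shape and show only what could happen.

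A common interval is a fair trade-off that the investigators may take or leave, not a correction. A straight-line adjustment is not a safe substitute, since it raised mean absolute error from 0.082 to 0.106 of the plateau on the assumed grid; it could be no more than exploratory.

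What is left is missing detail of the kind a study team settles in its working procedures: when baseline is taken, how many sham cycles are run, and the clock time of each battery. The two gas labels in the sham line contradict each other and must be reconciled by the investigators. Settling them would not remove the timing difference among A, B and C.

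### The plan names no scheme to balance session order over visits and predecessors, and no visit term in the model; specifying both would recover precision at little cost

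*Combined protocol and SAP*

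**What the plan says.** Section 6 (Research Plan) describes a four-period crossover. "Each participant will complete 3 different protocols of AIH delivery based on protocols derived from the literature", and each also completes a sham, listed under Intervention as "D. Sham hyperoxia (normoxia) for 2 minutes, normoxia to hyperoxia 1 minute". On spacing: "Each delivery and testing session will last approximately 2 hours and be separated by at least 24 hours". On allocation, the Intervention text says "The order of the protocol will be randomly assigned for each participant", with participant and outcome assessor blinded. It describes no sequence list, Latin square or blocking.

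Under Outcomes, every session has its own baseline: "Measures will be assessed at the hand and foot at baseline, immediately post- and every 10 minutes for 60 minutes after the AIH protocol". The analysis paragraph at the end of section 6 reads: "We will test effects protocol using a two way (protocol and time) analysis of covariance with sensory measures as the dependent variables". The only further terms it mentions are covariates: "Demographic variables that show an association with the sensory measures in our sample". Visit number, sequence and preceding condition do not appear. No sample size is given anywhere.

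**The concern.** Pain threshold and tolerance depend on when the participant says that a sensation has changed or has become too strong, and they are measured again at each of four visits. A drift across visits from familiarity or habituation is plausible, although the documents do not give its size. The protocol itself shows participants the heat range beforehand, partly to familiarise them and ease anxiety.

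As written, neither the allocation nor the model deals with such a drift. With independent draws from the 24 possible orders, sham may fall earlier or later on average than an AIH protocol, and the drift then enters that contrast as extra noise. Some conditions may also never directly follow certain others. A visit term can still be added before analysis, but a predecessor pair that never occurred cannot be recovered. The sequence list therefore has to be settled before enrolment.

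**Working it through.** The plan has no figure of its own to reproduce: it states no sample size, SD, effect size or alpha.

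**Inputs from the documents.** Four conditions, each given once to every participant; order random per participant; a model with protocol and time plus demographic covariates.

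**Assumptions.** Orders are drawn independently and uniformly from the 24 permutations; n = 8, 12, 24 or 40; participant is fitted as a factor; residual within-person SD σ = 1 per session; any drift is linear, d SD per visit; no dropout.

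**1. Imbalance in visit position.** The position of one condition is uniform on 1 to 4, with variance (16 − 1)/12 = 1.25. The covariance between two conditions is −1.25/3 = −0.4167. The difference in position therefore has variance 2(1.25) + 2(0.4167) = 10/3 per participant, and the difference in mean position has SD √((10/3)/n). Its expected value is zero. The other columns of the table come from simulated allocations; repeat runs agree to within about two percentage points.

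| Assumed n | SD of AIH − sham mean position (visits) | At least one AIH protocol ≥ 0.5 visit from sham | Some ordered predecessor pair never occurs | Mean excess contrast variance vs Williams, visit fitted |
|---|---|---|---|---|
| 8 | 0.65 | 86% | 74% | 18% |
| 12 | 0.53 | 73% | 32% | 11% |
| 24 | 0.37 | 44% | 1% | 5% |
| 40 | 0.29 | 22% | about 0% | 3% |

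In terms of participants, the last column means that random order with visit fitted is worth about 8/1.18 = 6.8, 12/1.11 = 10.8 and 24/1.05 = 22.9 participants on a Williams square.

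**2. Visit not fitted.** Without drift, a contrast has variance 2/n. Drift adds d²(10/3)/n under random order, so the ratio is 1 + (10/3)d²/2:
- d = 0.2: 1 + 3.333 × 0.04/2 = 1.07
- d = 0.3: 1 + 3.333 × 0.09/2 = 1.15
- d = 0.5: 1 + 3.333 × 0.25/2 = 1.42

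n cancels, so this proportional loss does not shrink in a larger trial.

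**3. Bias or noise.** In simulations with d = 0.3 and 0.5, random order and no visit term, the 5% test rejected a true null 4.3% to 5.7% of the time. At n = 8 and d = 0.5 the model standard error (0.589) matched the true SD of the contrast (0.592). The ordinary error term already carries the imbalance.

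**4. What the fix delivers.** A Williams square with n a multiple of four puts each condition at each visit n/4 times and gives each of the 12 ordered pairs n/4 times. The position difference is 0 and the contrast variance is 2σ²/n. At n = 8 and d = 0.5:
- *Williams, visit not fitted:* the true SD is √(2/8) = 0.50, but the drift stays in the residual. Its sum of squares is n × 5d² = 8 × 1.25 = 10 on 3(n − 1) = 21 degrees of freedom, so the residual variance is about 1 + 10/21 = 1.48 and the standard error about √(2 × 1.48/8) = 0.61. Simulation gave 0.60, with 2.0% rejection of a true null.
- *Williams, visit fitted:* standard error 0.49, rejection 4.4%.

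The list without the visit term improves the estimate but not the test.

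**The case against.** Four stronger readings are tempting, and the documents do not support them.

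- **That the plan rejects balanced sequences.** It is silent. Randomising each participant to a row of a Williams square would also fit the sentence. What stands is that a site following this text has no instruction to balance; if such a list exists, the sponsor need only say so.
- **That the trial is small.** No sample size is stated. The missing-pair problem depends heavily on n, falling from 74% at n = 8 to 1% at n = 24.
- **That chance imbalance biases the AIH-minus-sham contrasts.** Its expectation is zero, and step 3 shows that the test keeps its level. Random order is a valid design; its cost is precision.
- **That carryover is shown to be present.** Nothing in the documents says that sensory effects outlast the 24-hour minimum gap, although the gap is not justified either, and the plan makes no carryover estimate that missing pairs would defeat.

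There is also partial mitigation. Each session's baseline could absorb much of a shift in level between visits, and presenting the heat range beforehand may reduce a familiarity trend. But the analysis paragraph does not say that the session baseline is used as a covariate, and a baseline would not remove a visit effect on the response to the intervention itself. The drift sizes used here are assumptions.

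**Conclusion.** The point holds as a loss of precision from an under-specified allocation and a model without visit. If orders are drawn independently, the contrast variance with visit fitted is about 18%, 11% and 5% higher than under a Williams square at assumed n = 8, 12 and 24, and about 3% higher at n = 40, where it is minor. If visit stays out of the model, the excess is 15% to 42% for an assumed drift of 0.3 to 0.5 within-person SD per visit, and nil if there is no drift. Missing predecessor pairs matter only at very small n. The point does not show that the planned comparisons would be biased or invalid. The change is worth making because it needs no extra participants or sessions, and because the sequence list cannot be repaired after enrolment.

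**What to change.** In section 6 (Intervention), replace the sentence on order with wording such as: *Participants will be randomised in blocks of four to the four sequences of a Williams design for conditions A–D, so that within each block every condition occurs once at each visit and directly follows every other condition once. The list will be generated in advance and concealed from participants and the outcome assessor.* One such set is ABDC, BCAD, CDBA, DACB.

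In the analysis paragraph, add visit (1 to 4) as a factor alongside protocol and time. Also state the planned sample size and whether the session baseline enters as a covariate.

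The cost is two sentences and a pre-generated list. Enrolment is best in multiples of four, dropout slightly disturbs the balance, and visit uses three degrees of freedom (at n = 8, 18 instead of 21 for the residual).
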